#### **4.5. Secondary endpoint(s)**

The secondary endpoints are:

- Occurrence, intensity and duration of solicited AEs in the study participants at the administration site and solicited systemic AEs with an onset during the 4-day follow-up period after each vaccination (i.e., the day of vaccination and 3 subsequent days).

- Occurrence of unsolicited AEs in the study participants with an onset during the 30-day follow-up period after each vaccination (i.e., the day of vaccination and 29 subsequent days).
- Occurrence of SAEs in the study participants from the day of vaccination until 6 months. However, certain conditions will be excluded from this monitoring, to ensure that reporting is focused on relevant safety issues. The decision for this is based on the overall higher prevalence of certain conditions in the older age group. This includes but is not limited to falls, fractures, and the onset of tumors. A list of events that can be excluded is explicitly defined in the study protocol (see section 9.3.2). Such events are considered expected in an older patient population (>80 years). These do not need to be reported as SAEs unless there is an indication of a relationship with the investigational drug.
- Occurrence of pIMDs in the study participants from the day of vaccination until 6 months. A list of possible conditions that could qualify as pIMDs is added in section 18.
- Occurrence of any fatal SAEs in the study participants from Day 1 up to study end.

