**Table 1 Visit schedule and planned activities**

Procedure	Inclusion/exclusion criteria	Informed consent	Medical history/concomitant medications	Targeted physical examination o	Vital signs †	Blood draw	Adverse Events	Vaccine
V0*	√	√	√	√				
V1(D0) (up to +10 days to V0)					√	√	√ (D0 of diary) §	√
V2 (D1)						√		
V3 (D7) (+/- 1 day)						√	√ (collect diary) §	
V4 (D31) (+/- 3 days)						√	√	
V5 (3m)						√		

(+/- 14 days)							
V6 (6m) (+/- 14 days)					✓	✓	
V7† (12m) (B1) (+/- 14 days)			✓	✓	✓	✓ (D0 of diary) §	✓
V8 (B1D1)					✓		
V9 (B1D7) (+/- 1 day)					✓	✓ (collect diary) §	
V10 (B1D31) (+/- 3 days)					✓	✓	
V11 (B1 6 m) (+/- 14 days)						✓	

V = Visit; D = day; m = month; w = weeks; B1 = revaccination

\*V0 is the baseline visit: can be done at the same time as Visit 1(V1). Visit 1 will be the date of prime vaccination and start of the safety monitoring activity. V1 can be delayed to V0 for up to 10 days.

†Targeted physical examination includes determination of frailty status of the patient, body weight and body height.

†Visit 7 will be the date of the revaccination (B1) with sampling prior to vaccination (12-month prime vaccination timepoint).

‡Vital signs that will be obtained include blood pressure, pulse and body temperature.

§Diaries will be given to the study participants upon vaccination (V1 and V7) to note down any solicited AEs (local and systemic) for the 4-day follow-up period and will be recollected at the next study visit (V2 and V8)

For the trial, different medical parameters and vital signs will be measured at V0/V1 and V7. Medical history and concomitant medications will be noted to get an overview of the prevalence for certain co-morbidities. Targeted physical examination will include determination of a frailty index (using the Clinical Frailty Scale [CFS]), measurement of the body weight and the body height. Vital signs include blood pressure, pulse and body temperature.

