## **6. Participant selection**

Participants in the study will be enrolled as part of one of two age categories (60-65 years, and equal or older than 80 years). The goal is to have a similar ratio between male and female participants in both subgroups. Participants from both community dwelling and long-term care facilities will be enrolled in the study. Study participants will be enrolled at two different sites. The younger age group (60-65 years) representing community dwelling individuals will be enrolled at Studieenheteren Akademiskt Specialistcentrum, Region Stockholm. Participants in the older age group (80 years and above) will be enrolled from long-term care facilities at Familjeläkarnas Särskilda boenden (SÄBO).

Adherence to the inclusion criteria as specified in the protocol is essential. Inclusion criteria deviations are not allowed because they can jeopardize the scientific integrity or regulatory acceptability of the study or participant safety. All participants must satisfy all of the following criteria at study entry:

- Male or female individuals who were born between 1965 and 1960 or 1945 and before, who live in the community or in a long-term care facility.
- Individuals who can understand and read Swedish.

- Individuals who can provide written consent and agree (by written consent) to receive the RSV vaccine.
- Participants who, in the opinion of the investigator, can and will comply with the requirements of the protocol.
- Participants who are medically stable in the opinion of the investigator at the time of first vaccination. Participants with chronic stable medical conditions with or without specific treatment, such as diabetes, hypertension or cardiac disease, are allowed to participate in this study if considered by the investigator as medically stable.

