## 8.2. Methods for measurement of endpoints for clinical safety

To assess reactogenicity of the vaccine, all solicited AEs will be recorded over the 4-day follow-up period after each vaccination. The AEs will be reported by the study participants on standardized diary cards and information will be collected by the respective study personnel. Solicited AEs include:

- Injection site pain
- Injection site erythema
- Injection site swelling
- Fever (similar definition as described in section 6.2.)
- Headache
- Fatigue
- Myalgia
- Arthralgia

Grading of intensity of solicited AEs will follow the description in section 18.2.

To assess safety, all unsolicited AEs with an onset during the 30-day follow-up period after each vaccination (i.e., the day of vaccination and 29 subsequent days) will be recorded.

To assess safety, any SAEs or pIMD will be recorded from the day of vaccination until up to 6 months after vaccination.

Fatalities will be recorded throughout the whole study period.

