### **9.3. *Reporting and registration of Adverse Events***

Reporting of AEs will follow standard procedures, including follow-up on reactogenicity for 4 days after each vaccination for systemic and local solicited adverse events. Unsolicited AEs are reported for 30 days following each vaccination while SAEs are reported for 6 months following each vaccination. Follow-up of fatalities is carried out throughout the whole study period.

AEs that occur during the trial and not excluded from follow-up, which are observed by the investigator/trial nurse or reported by the participant will be registered in the CRF regardless of whether they are assessed as related to the investigational medicinal product or not. Assessment of causal relationship,

severity, and whether the AE is considered to be an SAE will be made by the investigator directly in the CRF (RedCap) or on a trial-specific worksheet. At minimum, for each AE/SAE, a description of the event is recorded (diagnosis/symptom if diagnosis is missing), start and stop dates, causal relationship, severity, if the AE is considered to be an SAE, measures and outcome.

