## **9.4. Follow-up of Adverse Events**

Study participants who have been reported with AE/SAE/SUSAR or AESI will be followed up until the condition has resolved or remains stable/persistent and even if the study period has ended.

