## 18.2. Grading of solicited AEs

**Table 6 Grading of solicited AEs as applied in this study**

Event	Intensity grade	Parameter
Pain at the injection site	0	None
	1	Mild: Any pain neither interfering with nor preventing normal everyday activities
	2	Moderate: Painful when limb is moved and interferes with every day activities
	3	Severe: Significant pain at rest. Prevents normal everyday activities
Headache	0	None
	1	Mild: Headache that is easily tolerable
	2	Moderate: Headache that interferes with normal activity
	3	Severe: Headache that prevents normal activity
Fatigue	0	None
	1	Mild: Fatigue that is easily tolerated
	2	Moderate: Fatigue that interferes with normal activity
	3	Severe: Fatigue that prevents normal activity
Myalgia	0	None
	1	Mild: Myalgia that is easily tolerated
	2	Moderate: Myalgia that interferes with normal activity
	3	Severe: Myalgia
Arthralgia	0	None
	1	Mild: Arthralgia that is easily tolerated
	2	Moderate: Arthralgia that interferes with normal activity
	3	Severe: Arthralgia that prevents normal activity
Erythema the injection site		Record greatest surface diameter in mm
Swelling at the injection site		Record greatest surface diameter in mm
Temperature*		Record temperature in °C/°F

\* Fever is defined as a temperature  $\geq 38.0^{\circ}\text{C}/100.4^{\circ}\text{F}$  by any route. The route for measuring temperature can be oral, axillary or tympanic.

The investigator will assess the maximum intensity that occurred over the duration of the event for all unsolicited AEs (including SAEs) recorded during the study. The assessment will be based on the investigator's clinical judgment. The maximum intensity of local injection site erythema/swelling and fever will be scored as follows:

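### Table 1 names two different visits for collecting the diary, and the one in its footnote (day 1) falls inside the four-day solicited-AE window

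*Protocol*

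**What the plan says.** Table 1 in Protocol section 5.2 deals with the diary in two places. The adverse-event cells for V1 and V7 mark D0 of the diary. Those for V3 (D7, within 1 day either way) and V9 (B1D7, same window) read "collect diary" and carry the footnote symbol. The V2 (D1) and V8 (B1D1) rows show a blood draw and no adverse-event entry.

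The footnote behind that symbol says diaries are handed out at V1 and V7 to note solicited events "for the 4-day follow-up period and will be recollected at the next study visit (V2 and V8").

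Section 4.5 defines the secondary reactogenicity endpoint as the occurrence, intensity and duration of solicited events "with an onset during the 4-day follow-up period after each vaccination (i.e., the day of vaccination and 3 subsequent days"). Section 8.2 makes the diary the reporting instrument ("The AEs will be reported by the study participants on standardized diary cards") but names no collection visit. In section 18.2, Table 6 has erythema and swelling entered as a measurement ("Record greatest surface diameter in mm") and fever as a temperature; Table 7 grades all three from those values.

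**The concern.** The cell and its own footnote give different visits for the same act. The footnote also conflicts with itself, because a four-day diary cannot be complete when it is taken back on D1.

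Table 1 is the schedule that site staff work from. Anyone following the footnote would remove the reporting instrument of a secondary endpoint partway through its window. Onsets on D2 and D3 would then have no prospective record, and neither would the later course of events that began on D0 or D1. Duration is exposed in particular: section 3 gives median durations of 2 days for local reactions and 1 to 2 days for systemic ones, so an event starting on D1 may well still be running when the diary is collected.

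Section 6 enrols the 60-65 group at one site and says "Participants in the older age group (80 years and above) will be enrolled from long-term care facilities". If the two sites read the table differently, the difference in data capture would coincide with age group. This is only a possibility; nothing in the protocol indicates that it will happen.

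**Working it through.** The protocol gives no figure to reproduce. The check is a day count.

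**Inputs**
- Solicited window: vaccination day plus 3 days (section 4.5) = D0, D1, D2, D3 = 4 days.
- Footnote collection visits: V2 = D1 and V8 = B1D1 (Table 1).
- Cell collection visits: V3 and V9 = D7 ± 1 = D6 to D8 after the dose concerned (Table 1).
- Solicited events (section 8.2): pain, erythema, swelling, fever, headache, fatigue, myalgia, arthralgia = 8.

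**Coverage after each dose**

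| Reading | Collected on | Window days the diary can hold | Window days missed |
|---|---|---|---|
| Footnote (V2, V8) | D1 | at most 2 (D0, part or all of D1) | at least 2 of 4 (D2, D3) |
| Cells (V3, V9) | D6 to D8 | 4 (D0 to D3) | 0 |

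Under the cell reading the window has already closed at the earliest permitted visit: 6 − 3 = 3 days after D3. At the latest permitted visit the margin is 8 − 3 = 5 days.

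**Recall gap if the footnote is followed**

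The next adverse-event contact in Table 1 is V3 or V9.
- Shortest gap: D6 − D3 = 3 days.
- Longest gap for D2-D3: D8 − D2 = 6 days.

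**Events graded from a measurement**

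Erythema and swelling (mm) and fever (temperature) make 3 of 8. A D2 or D3 value not written down at the time cannot be taken again at D6 to D8. The other five are graded by how far they are tolerated or interfere with activity, which a participant can describe afterwards, though less reliably.

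**Which reading fits the rest of the protocol**
- For D7: the cell entries, the empty adverse-event cells at V2 and V8, the window in section 4.5, and the footnote's own mention of four days.
- For D1: the footnote's visit numbers and its reference to the next visit. V2 and V8 are indeed the next visits after V1 and V7, so that phrase agrees with the numbers and gives staff reading only the footnote no sign of an error.

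**The case against.** The case for giving this little weight is reasonable. Almost everything in the table points to D7, so a careful coordinator would recover the intended reading. The loss is conditional on a site following the less plausible instruction, and nothing suggests that either will. The diary card and the site procedures were not available for this review and may state the collection day.

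Even if the diary is taken early, V3 and V9 carry an adverse-event check. Section 9.3 requires each event to be recorded with "start and stop dates, causal relationship, severity, if the AE is considered to be an SAE, measures and outcome", and section 9.4 says participants with reported events "will be followed up until the condition has resolved or remains stable/persistent". Occurrence and duration are therefore partly recoverable; what is lost is the prospective diary record. The endpoint is secondary, and section 10.2.1 reports it descriptively as counts and percentages in both age groups.

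All of this stands as a limit on the size of the problem. It does not remove the contradiction: both statements are current text, both name their visits explicitly, and nothing else in the protocol decides between them. General event recording also does not replace a measurement of diameter or temperature that was never noted.

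**Conclusion.** The footnote is wrong as written and should be corrected. It is very probably a slip, but it is an explicit instruction in the visit schedule. If followed, it leaves at least 2 of the 4 diary days unrecorded after each dose, with recall 3 to 6 days later as the substitute, and 3 of the 8 solicited events then depend on measurements that cannot be repeated. If both sites follow the table cells, the loss is zero.

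The number of participants affected cannot be derived from the protocol. The consequence is a weakened secondary reactogenicity endpoint, not a lost one. A distortion of the age comparison would further require the two sites to act differently. The primary D31 titre endpoint is not affected. Confidence is high for the contradiction and the day counts; how the sites would act is unknown.

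**What to change.** Reword the Table 1 footnote so that diaries are collected at V3 and V9, in line with the table cells and the four-day window. The reference to the next study visit has to go as well as the visit numbers, because V3 and V9 are not the next visits after V1 and V7. Give both sites the same written instruction that participants keep the diary until the D7 visit, and check that the diary card and any site procedure agree.

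The cost is one footnote correction and one site instruction. No visit, procedure or participant burden is added.

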**Table 2 Immunological read-outs at the different study visits**

Type of contact and time point	Sampling time point	No. of samples (Total)	Component	Priority rank
Prime vaccination				
Visit 1 (D0)	Pre-Dose 1	~65-70	RSV A neutralizing titers	1
			RSV B neutralizing titers	2
			RSVPreF3-specific IgG antibody	3

Visit 2 (D1)	Post Dose 1	~65-70			
Visit 3 (D7)	Post Dose 1	~65-70	RSV A neutralizing titers	4	
			RSV B neutralizing titers	5	
			RSVPreF3-specific IgG antibody	6	
Visit 4 (D31)	Post Dose 1	~65-70	RSV A neutralizing antibodies	1	
			RSV B neutralizing antibodies	2	
			RSVPreF3-specific IgG antibody	3	
Visit 5 (3m)	Post Dose 1	~65-70	RSV A neutralizing antibodies	1	
			RSV B neutralizing antibodies	2	
			RSVPreF3-specific IgG antibody	3	
Visit 6 (6m)	Post Dose 1	~65-70	RSV A neutralizing antibodies	1	
			RSV B neutralizing antibodies	2	
			RSVPreF3-specific IgG antibody	3	

Revaccination					
			RSV A neutralizing antibodies	1	
			RSV B neutralizing antibodies	2	
			RSVPreF3-specific IgG antibody	3	
Visit 7 (12m)	Pre-Dose 2	~65-70			
Visit 8 (B1D1)	Post Dose 2	~65-70			

Visit 9 (B1D7)	Post Dose 2	~65-70	RSV A neutralizing antibodies	4
			RSV B neutralizing antibodies	5
			RSVPreF3-specific IgG antibody	6
Visit 10 (B1D31)	Post Dose 2	~65-70	RSV A neutralizing antibodies	1
			RSV B neutralizing antibodies	2
			RSVPreF3-specific IgG antibody	3

\*Baseline measurement

In case of insufficient blood sample volume to perform all assays, the samples will be analyzed according to the priority ranking provided in Table 2.

### 5.3. Biological sampling procedures

#### 5.3.1. *Handling, storage, and destruction of biological samples*

Detailed sampling and handling procedures are described in a separate document. Collected biological samples will be used for protocol-mandated research and purposes related to the improvement, development and quality assurance of the laboratory tests described in this protocol. Future findings may make it desirable to use the samples acquired in this study for future research not described in this protocol. Therefore, all participants will be asked to give a specific consent to allow the sponsor or a contracted partner to use the samples for future research. Sample testing will be done in accordance with the recorded consent of the individual participant.

Throughout the trial 10 blood draws per participant are planned. Blood samples

(15-40 mL) will be collected at each time point (day 0, day 1, day 7, day 31, month 3, month 6, and month 12 after prime as well as day 1, day 7, and day 31 after revaccination) by venipuncture at the authorized clinical trial site. For PBMC isolation up to 4 EDTA tubes (or similar) of 8 mL will be drawn at each timepoint. In addition, one serum tube with a volume of 5 ml will be drawn.

A full overview of all samplings including volumes, types of samples and planned assays will be made available as an annex to this study protocol.

The sampling will be carried out by trained and experienced personnel and in a specific sampling order. Samples will be labelled accordingly and transported to the principal investigator. SOPs for sampling and handling are in place and clearly communicated prior to study start. SOPs for sample processing and storage will be prepared and used throughout the trial.

Serum and plasma samples will be used for enzyme-linked immunosorbent assay (ELISA)-based measurements of antibody titers against different pathogens. Appropriate methods are in place at the laboratory of the principal investigator. Approved and accredited methods from external laboratories might be used for validation.

Measurements of neutralizing titers against RSV A and RSV B as well as serum levels of RSV preF3-specific IgG will be performed by GSK using validated methods. In addition, neutralization assays established in the laboratory of the principal investigator can be used for measurements of neutralizing antibody titers against other respiratory viruses.

### 5.3.2. *Total volume of blood per participant*

A total of 10 blood draws per participant is planned for this clinical trial over the course of 13 months. Per timepoint a maximum volume of 40 mL blood will be taken. A blood sample will be taken from all participants at each visit. The overall volume of blood that will be collected during the entire study period is ~308 mL (4x ~40 mL, 2x ~37 mL, 2x 21 mL, 2x ~16 mL).

**Table 3 Overview of blood draws and planned volumes**

Visit	Prime						Revaccination			
	1	2	3	4	5	6	7	8	9	10
Time	D0	D1	D7	D31	3m	6m	12m	B1D1	B1D7	B1D31
Blood	32 mL	8 mL	32 mL	32 mL	16 mL	16 mL	32 mL	8 mL	32 mL	32 mL
Serum	5 mL	5 mL	5 mL	5 mL						
	■■■■■	■■■■■	■■■■■	■■■■■	■■■■■	■■■■■	■■■■■	■■■■■	■■■■■	■■■■■
Total	40 mL	16 mL	40 mL	37 mL	21 mL	21 mL	40 mL	16 mL	40 mL	37 mL

### 5.3.3. *Laboratory assays*

Laboratory assays are summarized in Table 4. Please refer to section 8.1. for a brief description of the laboratory assays summarized here and performed in this study.

**Table 4 Laboratory assays planned in this study**

CMI = Cell-mediated immunity; GSK = GlaxoSmithKline Biologicals S.A.; ICS = Intracellular cytokine staining; N/A = Not applicable; PBMC = Peripheral blood mononuclear cell; PreF = prefusion protein; RSV = Respiratory syncytial virus.

\*Certain analyses will be carried out by subcontractors employed by GSK.

A list of (clinical) laboratories used for sample analysis are provided in a separate document accompanying this study protocol, including address and information on analyses carried out by them.

Additional exploratory testing on collected samples might be done to gain a better understanding of the vaccine, of the clinical study data and/or of the disease or other diseases, to inform the development of other investigational products or to support development of vaccine-related assays, should such assay(s) become available at Karolinska Institute's laboratory, or a laboratory designated by Karolinska Institute. These assay(s) may not be represented in the objectives/endpoints of the protocol and will be described in ancillary study protocol(s), as needed. GSK clinical laboratories have established a Quality

System supported by procedures. The activities of GSK clinical laboratories are audited regularly for quality assessment by an internal but laboratory-independent Quality Department. Certain assays will be carried out by subcontractors outside of the European Union that have been selected by GSK. The Informed Consent Form states that samples will be sent to collaboration partners outside the EU or EEC.

GSK will be responsible for providing certain assay components including proteins such as RSVPreF3 for different assays including but not limited to antigen-specific cell probing and ELISA.

#### **5.3.4. *Biobank***

All samples taken in this trial, covered by the Biobank Act, are registered in a biobank and handled according to the current national laws and regulations. The samples are coded to protect the participant's identity. All samples and the identification/code list are stored securely and separately to prevent access by unauthorized persons.

### **5.4. Start, end, temporary halt and early termination**

#### **5.4.1. *Start of the clinical trial***

The start of the trial is defined as the start of screening activities. Sponsor will report the start of the trial in Sweden through notification in the Clinical Trial Information System (CTIS) within 15 days.

